Study drug tolerance will be assessed by obtaining serial measures of the Gastrointestinal Symptom Rating Scale (GSRS) every two weeks during the 12-month placebo or probiotic regimen²¹. These will be obtained with in-person interviews at the baseline and month 6 and 12 visits and by telephone contact with all subjects by the study coordinator every 2 weeks. Data will be analyzed within the 5 symptom domains depicting symptoms related to gastric reflux, abdominal pain, indigestion, diarrhea, and constipation. A GSRS total score, the sum of all 5 domains, will also be assessed. To our knowledge there is no published absolute or change in the GSRS score that is demonstrative of intolerance to a study drug or other treatment²¹⁻²³. Therefore we will *a priori* define intolerance to the study drug as a 50% increase in the total GSRS score from baseline at any two consecutive time points, or the new onset of a GSRS classifier score of 2 or 3 in at least three of the 15 gastrointestinal symptoms queried. If either of these signs of intolerance occurs, we will offer the subject the options of: 1) discontinuing from the study; 2) discontinuing the study drug but participating in the serial assessments (e.g. blood draws, DXA) in the research center, or 3) decreasing the dose of blinded study drug to one sachet/daily, with the option of resuming the two sachet/day study regimen upon resolution of symptoms. If intolerance symptoms recur, the same strategy will be followed. All episodes of intolerance to study drug and the twice-monthly GSRS data will be recorded by the study coordinator in the individual subject case report forms (CRFs) (see below).

Compliance with the study placebo or VSL#3 doses will be assessed serially. This will be determined by contacts (twice monthly telephone or at research center visits) of the study coordinator with each subject and responses to three standardized question areas: 1) "Are you having any difficulty, problems or new symptoms with the study medication?" 2) If yes, "What has the problem been?" and 3) "Have you missed any of your study drug doses, and if so how many in the previous 2 week period?" Appropriate notations based on subject responses will be documented in the CRF. Subjects will be instructed at study entry and reminded via serial contacts to return all of their used and unused drug sachets at each CRN visit (6 months +/- 2 weeks and 12 months +/- 2 weeks after entry). Unused and used study drug sachets will be tallied and recorded in the CRF by the study coordinator serially for the entire study. All sachets (used and unused) will be given to the Emory University Investigational Drug Service (IDS) for disposal.

Recruitment and retention will be documented via conventional CONSORT criteria and documentation of missed study visits, missed telephone communications and compliance with study drug administration. All data will be maintained in the CRFs.

4.13. Sample size and power considerations: Longitudinal data from 380 postmenopausal women form the basis for estimating the sample size and power for lumbar spine BMD as the primary outcome endpoint. BMD at the lumbar spine was available at baseline and 6 and 12 months after baseline (883 measurements across the 3 time points). Mean baseline BMD was 1.108 g/cm² (within-subject standard deviation = 0.03 g/cm² and the standard deviation on change = 0.02 g/cm²). Assuming no decline on average in BMD in the VSL#3 treated group and a decline on average of 0.03 g/cm² in the control group and an estimated within-subject standard deviation in each group of 0.03 g/cm², the proposed sample sizes (n=20 postmenopausal women per group) will provide more than 85% power to detect a difference on change of 0.03 g/cm² at the two-sided 5% significance level if the true difference between treatment groups is 0.03 g/cm² (two-sided two-sample equal variance t-test).

4.14. Statistical analyses: Demographic data will be summarized with standard descriptive statistics. Repeated-measures analyses for each outcome (i.e., GSRS scale scores, BMD) will be performed with a means model via the SAS MIXED Procedure (version 9.4; SAS Institute, Cary, NC), providing separate estimates of the means by time on study (baseline, 1-year and 2-years) and treatment group. The model will include three predictors (treatment arm, time on study and the statistical interaction between treatment arm and time on study). A compound-symmetric variance-covariance form in repeated measurements will be assumed for each outcome and robust estimates of the standard errors of parameters will be used to perform statistical tests and construct 95% confidence intervals²⁴. The model-based means are unbiased with unbalanced and missing data, so long as the missing data are non-informative (missing at random, MAR). A P-value ≤0.05 will be considered statistically significant for the main effects (treatment and time on study) and for the treatment by time on study interaction effect from the repeated measures analysis. The statistical test for interaction between time on study and treatment will be the primary overall hypothesis test to determine whether an outcome in the two study groups changed in significantly different ways during follow-up (i.e., different temporal patterns over time). If a mean outcome in the two groups is consistently different or similar over time (i.e., no statistical interaction) then the main effect test for treatment will be used as the primary test of VSL#3 efficacy. If a significant interaction is detected, then t-tests will be used to compare the differences between the model-based intervention means at each time point and to compare differences over time within each treatment arm. Specific statistical tests will be done within the framework of the mixed effects linear model. Analyses will control for risk factors for osteoporosis, such as age, gender, race, BMI, habitual alcohol consumption, smoking, physical activity, and fracture history, as necessary. All tests will be 2-sided and a P value ≤ 0.05 will be considered significant.

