3. CRITERIA FOR PATIENT SELECTION

3.1 Inclusion criteria: 1) Willing and able to give written informed consent for participation in the study, 2) Age range 50-65 years, 3) Menopausal status (defined by >1 yr since last menstrual period or FSH level in the postmenopausal range), 4) Ambulatory, 5) Body mass Index (BMI) must be ≥ 18.0 and ≤ 32 kg/m² at screening, 6) Bone mineral density (BMD), expressed as T-scores, must be > -2.5 in the lumbar spine (L1-L4), the femoral neck, and the total hip, as measured by dual energy X-ray absorptiometry (DXA), 7) Commitment not to use any products that may influence the study outcome (see below), and 8) Ability to understand and comply with the requirements of the study.

3.2 Exclusion criteria: 1) Premenopausal status, 2) History of ≥ 1 previous atraumatic bone fractures after age 50; 3) Presence of established osteoporosis (T-score ≤ -2.5 , in the lumbar spine, femoral neck or total hip as measured by screening DXA), 4) History of immunological or bone-related disorders including: HIV infection, Type I diabetes mellitus, bone marrow or organ transplantation; Inflammatory bowel disease (ulcerative colitis, Crohn's disease); multiple myeloma; osteomalacia; osteosarcoma; Paget's disease; rheumatoid arthritis; systemic lupus erythematosus; parathyroid disorders, 5) uncontrolled type II diabetes mellitus (HgbA1c $\geq 7\%$ within the last 12 months), 6) History of bariatric surgery or other forms of malabsorption (including documented celiac disease, or chronic diarrhea), 7) Alcohol abuse, 8) Clinically significant chronic kidney disease (stage ≥ 2 , with total serum creatinine level > 2.5 mg/dL and calculated glomerular filtration rate (GFR) < 60 mL/min by the Modification of Diet in Renal Disease (MDRD equation), 9) Clinically significant cardiovascular disease (myocardial infarction, cerebral vascular accident or acute congestive heart failure within the previous 12 months, 10) Any malignancies, other than localized skin squamous cell carcinoma, diagnosed within the previous 5 years, or any history of metastatic cancer, 11) History of use of oral supplement products containing probiotic bacteria (more than once per week) within four weeks prior to

Version 10/17/18

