The study will be conducted in a population of ambulatory, postmenopausal women aged 50-65 (BMI >18.5 and $\leq 30 \text{ kg/m}^2$), with a lumbar spine (L1-L4), femoral neck, and total hip BMD T-score > -2.5, as measured by DXA (see section 3 above). Women with osteoporosis (T score ≤ -2.5) will not be included in the study because at this stage of knowledge we find it unethical not to offer effective treatment to these individuals. We will recruit subjects of all ethnic groups. Covariates known to influence bone mass, including body mass index (BMI), history of smoking > 6 months prior to entry, alcohol use, baseline BMD of the lumbar spine, femoral neck and total hip area, bone fracture history and co-morbidities will be collected and controlled for in the final analysis. The primary endpoint is the change in bone mineral density (BMD) at the L1-4 lumbar spine over one year of study. Changes in BMD at the femoral neck and total hip area will be secondary endpoints. All BMD data will also be used as a tool for future studies power calculation and design. Additional endpoints will include changes in bone turnover markers and inflammatory/osteoclastogenic cytokines. These indices will provide much needed mechanistic information. To determine additional potential mechanisms of action of probiotics on health, we will conduct serial metabolomics analyses in the plasma, as well as serial assessment of plasma thiol/disulfide redox balance. The data will allow us to establish whether VSL#3 prevents bone loss and/or increases bone mass by regulating bone resorption, formation, or both. Based on our own data in mice following ovx, we hypothesize that treatment with VSL#3 will quickly decrease bone resorption and then stimulate bone formation, resulting in improved net BMD at least one site over the 12-month period of study.

4.2. Screening for eligibility: For study subjects identified among patients seen at the Emory-affiliated Endocrinology, Ob/Gyn, Rheumatology and General Medicine clinics, patients will be pre-screened for eligibility using the Emory Healthcare electronic medical record, and potentially eligible subjects will be approached during their clinic visit by a study coordinator or they will be contacted by phone or letter (as described above) to conduct a full screen. For potential study subjects identified outside of Emory-affiliated Clinics, potential subjects will contact the study team by phone and undergo a pre-screening discussion.

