4.6. Randomization and Stratification: Personnel in the Department of Biostatistics and Bioinformatics at Emory University have developed a centralized electronic randomization system that has been successfully used in several clinical studies¹⁶⁻¹⁹. Subjects will be blindly assigned in equal proportions, stratified by age (above and below 58 years) using a pseudo-random-number generator with randomly permuted blocks. These assignments will be stored in a backend database table within the iDataFAX database management system. This method serves to balance the treatment group assignments over the course of the study to ensure that the desired number of subjects will be allocated to each of the treatment groups at any time point during the randomization period. Permuted block sizes will not be disclosed to the blinded study personnel to minimize the likelihood of their being able to predict the next randomization assignment in the series. Briefly, after obtaining informed consent, all eligibility confirmation data will be entered into the web-based data management system by a research coordinator. If the patient meets all eligibility criteria, computer randomization will be performed and the coordinator will be provided with an audit trail of the process including a verifiable link between the unique study ID and treatment assignment. The application will be password protected with access restricted to designated personnel, including the EUH Investigational Drug Pharmacy staff pharmacist who **will dispense blinded study drug for subjects randomized to Arms A or B.**

4.7. Screening, Entry and Follow-up Evaluations: These will occur as outlined in Table 1. Adverse effects and safety data will be reviewed at least every 6 months by a Data Safety Officer, a gastroenterologist senior Emory faculty member with expertise in clinical trials who is unaffiliated with the study, as described below (Section 7.5).

4.8. Procedures to be performed (all for research purposes only):

- **Medical examination:** Medical history and medications will be reviewed by a member of the research team, and a physical exam will be completed by a licensed physician, as required by the clinical research unit. Habitual alcohol intake and dietary calcium intake (based on reported supplements, dairy, and other high-calcium foods) will be assessed.
- **Urine collection:** Urine will be collected for standard urinalysis indexes.

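### Randomisation is stratified by age at 58, but the stated primary model does not commit to the stratum, and optional adjustment for age is left without a form or a rule

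*Combined protocol and SAP*

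**What the plan says.** Section 4.6 (Randomization and Stratification): "Subjects will be blindly assigned in equal proportions", "stratified by age (above and below 58 years) using a pseudo-random-number generator with randomly permuted blocks". Section 3.1 sets the eligible range: "Age range 50-65 years".

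Section 4.14 (Statistical analyses) gives the model: "The model will include three predictors (treatment arm, time on study and the statistical interaction between treatment arm and time on study". No stratum term is listed. Later in that section: "Analyses will control for risk factors for osteoporosis, such as age, gender, race, BMI, habitual alcohol consumption, smoking, physical activity, and fracture history, as necessary". Section 4.1 also promises covariate control in the final analysis, in a list that begins "Covariates known to influence bone mass, including body mass index (BMI), history of smoking > 6 months prior to entry, alcohol use" and does not name age.

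On the test itself, section 4.14 states: "The statistical test for interaction between time on study and treatment will be the primary overall hypothesis test". If there is no interaction, "then the main effect test for treatment will be used as the primary test of VSL#3 efficacy". The model assumes compound symmetry and uses robust standard errors. Section 4.13 bases power on an unadjusted two-sample t-test and does not rely on the stratum.

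**The concern.** Stratified blocks keep the arms balanced on the age split, so age contributes little to the chance difference between arms. An analysis that leaves the stratum out still counts the variance due to age as noise. Its model-based standard error is then larger than the true variability of the estimate, and the test is conservative, provided that age predicts the outcome tested.

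The plan does not exclude adjustment for age. It leaves it to discretion: nothing says when adjustment is necessary, whether age enters as the 58-year split or as a continuous variable, or whether it interacts with time. In a trial of 40 women this leaves an analyst's choice open in the primary test. The interaction with time matters most, because the primary test concerns change and a constant difference in level between age groups cancels from change.

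A smaller gap is that the wording of the cut does not place a woman aged exactly 58.

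**Working it through.** **Inputs.** From section 4.13: 20 women per arm, difference in change 0.03 g/cm², SD 0.03 g/cm², two-sided 5%. From Table 1: DXA at baseline and 12 months. The documents give no figure for how well the age split predicts BMD change, so R² (the share of the within-arm variance of 12-month change explained by the stratum) is assumed at 0, 5%, 10% and 20%. Equal strata and complete data are also assumed.

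**1. The plan's power.** SE = 0.03 × √(2/20) = 0.00949; noncentrality = 0.03/0.00949 = 3.16; critical t on 38 df = 2.024. Power is 86.9% (88.5% by normal approximation), which agrees with the stated figure of more than 85%.

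**2. Which term matters.** Each woman's change is her 12-month value minus her baseline value, so a stratum effect that is constant over time drops out. One complete data set of 40 women was simulated with age affecting the level of BMD only:
- Adding a stratum main effect left the arm-by-time SE unchanged (model-based 0.00900 and 0.00900; robust 0.00877 and 0.00877).
- The SE of the arm coefficient, which compares levels as the fallback test does, fell from 0.0363 to 0.0320.

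A main effect can therefore help the fallback test, but only stratum-by-time can help the primary one.

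**3. Size and power for change, model-based SEs.** With balance within strata, the true SE is 0.00949 × √(1 − R²), while the unadjusted analysis estimates about 0.00949. The overstatement is 1/√(1 − R²). Approximate size is 2P(t₃₇ > 2.024/√(1 − R²)). The last columns come from 60,000 simulated trials per setting.

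| Assumed R² | SE overstated by | Size, formula | Size, simulated | Power unadjusted | Power adjusted | Difference (points) |
|---|---|---|---|---|---|---|
| 5% | 2.6% | 4.5% | 4.4% | 87.1% | 88.3% | 1.2 |
| 10% | 5.4% | 4.0% | 3.9% | 88.1% | 90.1% | 2.0 |
| 20% | 11.8% | 3.0% | 2.9% | 89.4% | 93.2% | 3.8 |

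At R² = 0, adjustment raises the critical value from 2.024 to 2.026, and power goes from 86.90% to 86.85%.

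**4. What these R² values mean.** With equal strata, the difference in mean one-year change between the age groups is 2 × 0.03 × √R² = 0.013, 0.019 or 0.027 g/cm².

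**5. The planned robust SEs.** Section 4.14 names no small-sample correction. An uncorrected sandwich SE with 20 per arm is √(19/20) = 0.975 of the usual one.
- Unadjusted, R² = 0: 2P(t₃₈ > 2.024 × 0.975) = 5.6%.
- Unadjusted, R² of 5%, 10% or 20%: simulated size is about 4.9%, 4.4% or 3.4%.
- Adjusted: the ratio is about √(37/40) = 0.962, so 2P(t₃₇ > 2.026 × 0.962) = 5.9%, or about 6% at every R².

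**6. Age exactly 58.** Ages 50 to 65 span 16 whole-year ages. If ages were uniform (an assumption), 40/16 = 2.5 women would be aged 58.

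**The case against.** A reader might infer that the standard errors are too large and that power is lost. The documents do not support this as a fact. It requires the age split to predict one-year change, and no such figure is given. The 20% case needs a difference of 0.027 g/cm² between age groups, nearly the whole assumed treatment effect of 0.03.

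Nor is the benefit of stratification thrown away. Unadjusted power rises with R² (87.1%, 88.1%, 89.4%), because balance improves the estimate even without adjustment, and every value exceeds the plan's 85%. The shortfall exists only against an adjusted analysis.

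The plan also names age first among its adjustment factors, so it would be wrong to say that it ignores age. And the conservatism is that of model-based SEs: with uncorrected robust SEs, the unadjusted test is close to nominal at R² = 5% and slightly anticonservative at R² = 0, while adding the stratum gives about 6%.

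Finally, a reader might conclude that women aged 58 belong to no stratum. Assignment is made by a central electronic system that may already code the boundary, and either coding leaves allocation random.

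All of this stands. It limits the point but does not remove it: the plan still does not commit to its one stratification factor, and does not say in what form age would enter.

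**Conclusion.** The point holds as a gap in specification with a modest, conditional cost. It does not threaten the trial's validity or its stated power. Under model-based SEs, equal strata and complete data, leaving out a stratum that explains 5% to 20% of the variance of change lowers size to between 4.4% and 2.9% and gives up about 1 to 4 points of power. If the stratum explains nothing, including it costs about 0.05 points. Power above 85% is met with or without the stratum under the plan's own SD. The case for the change is that it removes an open choice from the primary test and has little downside. With uncorrected robust SEs, it does not by itself bring size to 5%. The boundary at 58 is a wording gap with no shown effect on any result.

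**What to change.** In section 4.14, state that the primary BMD model always includes the randomisation stratum and stratum-by-time; for two time points this is equivalent to the stratum as a term in a model for 12-month change. The stratum main effect also serves the fallback treatment test. Apply the same terms to the secondary outcomes.

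In section 4.6, state which stratum a woman aged exactly 58 enters, matching how the randomisation system is coded, and use that definition in the analysis.

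The cost is about two sentences, one degree of freedom for the two-time-point change contrast, and up to three parameters for outcomes measured at three visits (one for stratum, two for stratum-by-time). If robust standard errors are kept, section 4.14 should also say whether a small-sample correction applies, since that choice moves size by about as much as the stratum does at low R².

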DXA scan: (lumbar spine, femoral neck, and total hip, total and regional body fat, total and regional lean body mass, visceral fat)*	x	x		x
Dietary Intake 3-day food record		x	x	x
BioElectrical Impedance Analysis (BIA) Body composition and total body water		x	x	x
Anthropometrics (height, weight, BMI, waist & hip circumference)				
Handgrip strength Hand-held dynamometer		x	x	x
Serum 25(OH)D	x			x
Stool microbiota composition		Xx	Xx	Xx
Plasma metabolomics		x	x	x
Plasma Amino thiols (GSH, GSSG, Cys, CySS)		x	x	x
Serum Intact PTH	x			
Complete blood count (CBC)	x		x	x
Chemistry profile	x		x	x
Urinalysis	x		x	x

*Note: First DXA scan will be done at the screening visit or the entry visit (not both).

4.5 Intervention: A total of 40 matched postmenopausal women meeting all specific inclusion/exclusion criteria will be blindly randomized to one of two study arms. **Arm A** (n=20): VSL#3 two active sachets [containing 450x10⁹ colony-forming units (CFU)/sachet], taken daily in a single administration; **Arm B** (n=20; control): two placebo sachets taken daily in a single administration. Thus, Arm A will receive 900 billion CFU daily and the control group (Arm B) will receive no supplemental probiotics (**Figure 1**).

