7.5.5.5 Quality Control

Quality control (QC) is the responsibility of all study personnel. QC covers all phases of the studies from developing good data collection instruments, to training of clinical center staff, and monitoring adherence to study protocols, procedures and progress of the studies. The quality control process includes data entry plus all data is reviewed for completeness and accuracy.

7.5.5.6 Training: The DCC will train clinical personnel in study procedures for data collection. Training will include providing instruction on completion of CRFs, use of the iDataFax system for data entry, data quality control via QC reports generated by iDataFax, and use of the web dashboard.

7.5.6 Policies and Methods for Ensuring Blinding of Study Results: Only the IDS pharmacy will know which study drug was given to the subject. The study team, parents, subjects, individuals entering the data, statistician, individuals performing laboratory tests and DXA scans, research center nurses and investigators will remain blinded as to which treatment the subjects received. Each subject will be assigned a unique identifier, which will be used in the database. In addition, all lab specimens will only include the patient's unique identifier. Permuted block sizes will not be disclosed to the blinded study personnel to minimize the likelihood of their being able to predict the next randomization assignment in the series. Investigators and all study personnel will remain blinded until the final subject has completed her final visit and primary and secondary endpoints have been analyzed.

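### Section 4.6, read literally, gives the coordinator who enters eligibility data a link from study ID to treatment, which contradicts the blinding policy in Section 7.5.6

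*Combined protocol and SAP*

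**What the plan says.** Section 4.1 describes the trial as double-blind. On the mechanics of allocation, Section 4.6 says "all eligibility confirmation data will be entered into the web-based data management system by a research coordinator". Once eligibility is met and the computer has randomised, "the coordinator will be provided with an audit trail of the process including a verifiable link between the unique study ID and treatment assignment". The same section stores assignments in a table within the iDataFAX system. It limits the application to designated staff, of whom the investigational pharmacist is given as one example, and withholds block sizes from blinded personnel.

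Section 7.5.6 sets the blinding policy: "Only the IDS pharmacy will know which study drug was given to the subject". It continues: "The study team, parents, subjects, individuals entering the data, statistician, individuals performing laboratory tests and DXA scans, research center nurses and investigators will remain blinded". All study personnel are to stay blinded until the last visit is complete and the endpoints have been analysed. The unique identifier is also the key used in the study database.

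Section 4.5 states what each arm receives: "Thus, Arm A will receive 900 billion CFU daily and the control group (Arm B) will receive no supplemental probiotics".

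Other sections describe a study coordinator's duties. Section 4.2 says that "potentially eligible subjects will be approached during their clinic visit by a study coordinator". In the tolerance paragraph of Section 4.10, GSRS scores are obtained at visits and "by telephone contact with all subjects by the study coordinator every 2 weeks", and "All episodes of intolerance to study drug and the twice-monthly GSRS data will be recorded by the study coordinator". The compliance paragraph that follows has the study coordinator ask about missed doses and count returned sachets.

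**The concern.** A person who enters eligibility data is given the means to connect a study ID to a treatment, while the blinding policy names data-entry staff and the study team as blinded and the pharmacy as the only party that knows. Staff following Section 4.6 as written would breach Section 7.5.6.

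Two things are at stake.

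- **Outcome collection.** If the coordinator of Section 4.6 is the study coordinator of Section 4.10, or shares access with that person, the interviewer for GSRS and adherence could know the arm. GSRS is one of the two outcomes named as examples in Section 4.14, and compliance is item 9 of the secondary endpoints. Meeting the intolerance definition leads to an offer to reduce or stop study drug, so biased recording could reach exposure as well as measurement.
- **Allocation concealment.** Block sizes are withheld so that staff cannot predict the next assignment. Sight of past assignments within an age stratum undercuts that safeguard, and Section 4.2 has a coordinator approaching potential participants.

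**Working it through.** **Comparing the sections.** The plan gives no figure to reproduce, so the main check is of wording.

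1. *Who receives the link?* In Section 4.6 it is the coordinator, and the only coordinator introduced there is the research coordinator who enters the eligibility data.
2. *Is that person blinded under Section 7.5.6?* Yes, on two counts: as someone entering data and as a member of the study team. Only the pharmacy is exempt.
3. *Is the link coded?* No section says so. Section 4.6 calls the assignment blind and the dispensed product blinded, but does not say what the audit trail displays. The access restriction does not exclude the coordinator.
4. *Would an A/B label be a mask?* No. Section 4.5 publishes what A and B are.
5. *Is the coordinator kept apart from outcome collection?* Sections 4.2 and 4.10 say study coordinator and Section 4.6 says research coordinator. Nothing states that they are different people or have different access.

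**Contacts that could be affected (upper bounds: no dropout, one role makes every contact).** Inputs: 40 women (Section 3.3), 12 months, and contacts described both as twice monthly and as every two weeks.

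- Contacts per woman: 2 × 12 = 24, or 52 / 2 = 26.
- Adherence contacts: 24 × 40 = 960 to 26 × 40 = 1,040.
- Telephone GSRS contacts, leaving out the month 6 and month 12 interviews, whose interviewer is not named: (24 − 2) × 40 = 880 to (26 − 2) × 40 = 960.

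**Predictability of the next assignment (illustration only).** Block sizes are undisclosed and stratum sizes are not given. I assume blocks of 2, 4, 6 or random mixtures of these, and two age strata of 20. The rule is to guess the arm with fewer assignments seen so far in the stratum, tossing a coin if tied. It needs no knowledge of block size.

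With all earlier assignments seen, complete blocks can be worked exactly as the average probability of a correct guess over positions:

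- Block of 2: (0.5 + 1) / 2 = 0.750.
- Block of 4: (1/2 + 2/3 + 2/3 + 1) / 4 = 0.708.
- Block of 6: (0.5 + 0.6 + 0.6 + 0.7 + 0.7 + 1) / 6 = 4.1 / 6 = 0.683. In a stratum of 20, three full blocks plus two further places give (3 × 4.1 + 0.5 + 0.6) / 20 = 0.670.

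Simulation (4,000 runs per setting) agrees and adds partial sight, where each earlier assignment is seen with probability 0.5:

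| Blocks | All seen | Half seen | None seen |
|---|---|---|---|
| 2 | 0.750 | 0.568 | 0.50 |
| 4 | 0.708 | 0.563 | 0.50 |
| 6 | 0.670 | 0.558 | 0.50 |
| 2/4 | 0.718 | 0.565 | 0.50 |
| 4/6 | 0.686 | 0.560 | 0.50 |
| 2/4/6 | 0.696 | 0.562 | 0.50 |

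**The case against.** The strongest reply is that this is loose drafting and the context favours a harmless reading. Section 4.6 refers repeatedly to blinding, a verifiable link in an audit trail need not display the decoded arm, and the dedicated policy in Section 7.5.6 is explicit. That reading is possible, but it is written nowhere. It therefore limits the finding to a conflict in the text without removing the conflict.

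The second reply is that harm is conditional: the link must be unmasked, the two coordinator roles must overlap or share access, and someone must act on the knowledge. The instruments also offer some protection. GSRS is a validated 15-question instrument answered by blinded participants. Intolerance follows a numerical rule fixed in advance: a 50% rise in total score at two consecutive time points, or new scores of 2 or 3 on at least three symptoms. Compliance includes a physical sachet count. GSRS is also absent from the numbered secondary endpoint list. These points stand and narrow the room for bias. They do not close it, because the numerical rule is applied to scores that are largely obtained and recorded by interview with the coordinator.

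The third reply is that the figures do not measure bias. That is correct: contact counts show how much data collection is exposed, not an effect on any endpoint. The 67–75% range needs sight of every earlier assignment in the stratum and applies only to the next slot. Entry may follow screening by up to 4 weeks, and up to 100 women may be screened for 40 places, so someone approaching a candidate could not readily know which slot she would fill. Many eligibility criteria are objective. Steering allocation is therefore possible but not shown to be likely.

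**Conclusion.** The point holds. As written, Section 4.6 cannot be reconciled with Section 7.5.6, and following it literally would break the double blind for a person the policy lists as blinded. Confidence is high on the contradiction. The documents do not show that anyone was, or would be, unblinded in practice.

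The consequences depend on an unmasked link and on overlap or shared access between the coordinator roles. Under those conditions, GSRS, intolerance episodes and compliance are the exposed data, and allocation could become partly predictable, to the degree shown above for the assumed blocks and strata. The DXA primary endpoint and the laboratory assays are less exposed, because Section 7.5.6 separately lists the staff who perform them as blinded. The inconsistency should be corrected, but it does not by itself undermine the primary endpoint.

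**What to change.** Rewrite the sentence in Section 4.6 so that the coordinator receives only confirmation that randomisation took place and a masked randomisation number. State that the audit trail and the link from study ID to treatment are visible only to the investigational pharmacy. If a system administrator must also hold the link, because assignments sit in an iDataFAX table, name that role as an exception in Section 7.5.6 so that the two sections agree. If what the coordinator sees is already coded, Section 4.6 should say so.

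The cost is one sentence in Section 4.6 and at most one clause in Section 7.5.6. Dispensing is unaffected: the pharmacist already has system access under Section 4.6, and the pharmacy supplies drug subject by subject under Section 5.4. The documents do not describe how access is configured, so any system work needed is unknown.
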